11.5.3 Pharmacokinetic / pharmacodynamic interactions

Not applicable.

11.5.4 Other assessments

Not applicable.

[figure not shown]

11.7 Sample size calculation

The sample size justification for this study is based on internal data from Part 2 of the LIK066 obesity PoC study (LIK066X2201) on the 50 mg tid treatment regimen.

For patients on the 50 mg tid regimen, a mean (range) of 3.5 (0-12), 4.8 (0-18), and 3.9 (0-18) daily episodes of diarrhea were observed for Days 1, 2 and 3, respectively, of which 3.2 episodes occurred between the 1st and 2nd dose on Day 1. If the true effect of the low carb diet or of the supplements is a reduction in the number of episodes per day from a mean of 3 episodes per day on the high carb diet to 1.5 episodes per day, or from a mean of 5 episodes per day to 3 per day, then 5 subjects per sequence per study part (30 subjects total) with complete data will provide 80% power to detect the reduction. Assuming a drop-out rate of 37.5%, 8 subjects per sequence (48 total subjects) should be enrolled.

These results are based on 1000 simulated trials. For each simulated trial, the number of daily diarrhea episodes was generated from a Poisson distribution, where period-specific means, adjusted by the treatment effect, share a common gamma-distributed random subject effect in order to reflect a correlation between observations from the same subject. Only a single observation per-period for each subject was generated, reflecting one day of treatment. Each trial was analyzed using the GLIMMIX procedure in SAS, using a negative binomial model with fixed effects of treatment and period and normally distributed random subject effects, and assuming no carryover effects from one period to the next.

Two plausible scenarios for the variability of the number of daily diarrhea episodes were considered: (1) assuming the variability is as was observed in LIK066X2201, reflected by a dispersion parameter in the negative binomial model of 2.4, and (2) assuming the endpoint is less variable, reflected by a dispersion parameter of 1. In both scenarios, the power for detecting the reductions is at least 80%. Simulations were also performed under two additional scenarios where non-zero period effects were assumed (a sequential increase/decrease of 0.1 in the log scale), and these also demonstrated sufficient power with 5 completers per sequence.

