11.4.2 Statistical model, hypothesis, and method of analysis

The primary analysis will be performed by study part. The daily number of diarrhea will be analyzed using a negative binomial mixed effects model with fixed effects of period, treatment, day, the period-by-day interaction, and the treatment-by-day interaction, and a random subject effect. An unstructured covariance matrix will be specified for the repeated observations on a subject within the same period. The least-squares mean and associated 80% CI for the number of diarrhea episodes per day for each treatment, and the estimated mean difference between each treatment, the p-value, and corresponding two-sided 80% CI, will be extracted from the model for each day, and summarized by a table and a line chart. Conclusions from the analysis will be based on treatment differences from all 3 days, collectively.

[REDACTED]

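### Must the 80% power in Protocol Section 11.7 be reworked because no significance level is given and within-subject variation is not simulated?

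*Protocol*

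**What the plan says.** Protocol Section 11.7 justifies 5 completers per sequence in each part by 1000 simulated trials. The target reductions are from 3 to 1.5 and from 5 to 3 daily episodes. Counts are "generated from a Poisson distribution, where period-specific means, adjusted by the treatment effect, share a common gamma-distributed random subject effect", and "Only a single observation per-period for each subject was generated, reflecting one day of treatment". Each trial is analysed "using a negative binomial model with fixed effects of treatment and period and normally distributed random subject effects".

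Two variability scenarios are used. One is described as "assuming the variability is as was observed in LIK066X2201, reflected by a dispersion parameter in the negative binomial model of 2.4"; the other sets the parameter to 1. The claim is "In both scenarios, the power for detecting the reductions is at least 80" per cent. Additional runs use period effects of plus or minus 0.1 on the log scale. The section names no significance level.

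For the analysis, Protocol Section 11.4.2 says that "An unstructured covariance matrix will be specified for the repeated observations on a subject within the same period". It reports estimates so that "the p-value, and corresponding two-sided 80% CI, will be extracted from the model for each day", and adds: "Conclusions from the analysis will be based on treatment differences from all 3 days, collectively". SAP Section 6.1.3 repeats this and words its hypotheses directionally, again without a level. Both documents call the study non-confirmatory.

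**The concern.** A power figure has no meaning without a level, and here the level decides the answer. A reader who assumes the usual 5% would take the study to be better powered than it is at that level.

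The variability scenarios also look weaker than they sound. The dispersion parameter enters only through one gamma effect shared by all of a subject's periods; given that effect, the counts are Poisson. A shared effect largely cancels when a subject is compared with himself or herself, so moving from 2.4 to 1 hardly tests the design. What limits a cross-over is variation within a subject beyond Poisson. The planned model allows for such variation, but the simulation contains none. Scenario (1) is presented as the variability seen in the earlier study, yet it places all of it between subjects.

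Finally, the simulation covers one day per period, while conclusions rest on three. If these points bit, the justification for 48 subjects would be unreliable.

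**Working it through.** **Inputs from Protocol Section 11.7.** Means 3 to 1.5 and 5 to 3; gamma variance 2.4 or 1; 5 completers in each of 3 sequences, so 15 per part; one count per period. **Assumed:** the third treatment also has the reduced mean (trying 2.1 or 3 in the 3 to 1.5 case moved power by about 1-2 points), and dispersion means the gamma variance, since 1 is called less variable.

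**Step 1. Closed form with no dispersion.** Power = Φ(|ln ratio|/SE − z), with SE = √(1/(15·m1) + 1/(15·m2)).
- 3 to 1.5: SE = √(1/45 + 1/22.5) = 0.258; 0.693/0.258 = 2.68.
- 5 to 3: SE = √(1/75 + 1/45) = 0.189; 0.511/0.189 = 2.71.

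With z = 1.96, 1.645 and 1.282 this gives about 77%, 85-86% and 92% at two-sided 5%, 10% and 20%.

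**Step 2. Reproduce the plan's figure.** One day, shared gamma effect, 15 subjects, 3000 trials per cell. Entries are for 3 to 1.5 / 5 to 3.

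| Fit | Dispersion | 5% | 10% | 20% |
|---|---|---|---|---|
| Negative binomial mixed model, Wald t, 26 df | 2.4 | 62/61% | 74/73% | 85/83% |
| | 1 | 68/68% | 80/79% | 88/89% |
| Conditional Poisson, Wald z | 2.4 | 67/67% | 76/77% | 85/85% |
| | 1 | 72/74% | 82/83% | 89/90% |

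At 20% the claim holds in both scenarios. With period effects of plus or minus 0.1 it still holds (82-87% for dispersion 2.4, 85-91% for 1). With 4 per sequence and dispersion 2.4, the conditional Poisson fit gives 77/78% at 20%. So 5 is the smallest number that works at that level, which strongly suggests that the sponsor used 20%. The drop-out step also reproduces: 5/(1 − 0.375) = 8 per sequence, and 8 × 3 × 2 = 48.

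**Step 3. Add within-subject variation.** Hold marginal dispersion at 2.4 by (1 + ks)(1 + kw) = 3.4, where ks is the subject variance and kw the within-subject variance. The documents give no kw, so a range is shown. All entries are at the 20% level.

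| Basis | kw = 0 | 0.1 | 0.25 | 0.5 |
|---|---|---|---|---|
| One day | 85/83% | 80/76% | 74/67% | 67/57% |
| Three-day total, kw independent by day | 98/98% | – | 97/94% | 95/87% |
| Three-day total, kw persistent through the period | 98/98% | 96/91% | 89/78% | 78/65% |

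A repeated-day model, with a random subject-by-period effect standing in for the unstructured covariance, agrees: 96/92% and 92/85% for independent kw of 0.25 and 0.5, and 89/79% and 78/63% for persistent kw. The three-day break-even for 80% is about 0.4 / 0.23 if kw persists, and above 0.5 for both reductions if it is independent by day.

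**Step 4. Accuracy.** Monte Carlo standard error is at most about 1.2 points. The actual level at nominal 20% was 16% with kw = 0 and 25-26% with kw of 0.25-0.5. The first column of Step 3 is therefore somewhat conservative, and the kw = 0.25 and 0.5 columns somewhat favourable. SAS GLIMMIX may estimate slightly differently.

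**Step 5. Margin not counted above.** Protocol Section 4 expects at least 36 completers, which is 36/2 = 18 per part if split evenly, or 6 per sequence. For dispersion 2.4 the conditional Poisson fit then gives 83/84% at 10% and 91/91% at 20%. Scaling the noncentrality by √(18/15) = 1.095 lifts the persistent 0.25 cell for 5 to 3 from 78% to about 83%, and the persistent 0.5 cell from 65% to about 71%.

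**The case for a change.** The strongest case for a change is that a sponsor who justifies 48 subjects by a power claim should make that claim readable, and the repair would be cheap: one phrase for the level and one re-run with a within-subject component. The scenarios do not show robustness to variation within a subject. On the plan's own one-day basis, a kw of only about 0.10 (3 to 1.5) or 0.04 (5 to 3) takes power down to 80%. If a larger kw persists through a period, power for 5 to 3 stays below 80% even with 18 completers per part.

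All of this is correct as description. The level is missing from the visible text, and the scenarios test less than they appear to. It does not show that a stated figure is wrong. The adverse three-day results need a variance that is both sizeable and persistent, and nothing in the documents supports or excludes it. A re-run could not settle this either: unless subjects in the earlier study had repeated courses, the persistent part cannot be separated from the subject effect, so the result would still rest on an assumed range.

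**Conclusion.** No change follows. The missing level is a gap that a reader can fill from the plan itself: every planned model-based estimate carries a two-sided 80% interval, and at the matching 20% level (one-sided 10%) the claim of at least 80% reproduces in both scenarios, with 5 per sequence as the smallest sufficient number. Section 11.4.2 also ends in a blacked-out block, so it cannot be established that the level is stated nowhere.

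The other two simplifications work in opposite directions. Omitting within-subject variation flatters the power; simulating one day instead of three understates it. Together they leave three-day power at about 98% with no such variation and above 80% in most of the cases examined. Shortfalls appear only with a persistent variance above roughly 0.4 or 0.23 at 15 completers per part.

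This rests on reading the level as 20%, on the third-treatment mean, and on assumed values of kw. A within-subject sensitivity run would be reasonable but optional. It would change no sample size, endpoint, model or conduct in a non-confirmatory study, and the SAP's document history shows the study already under way in September 2017. The reported intervals will show the precision actually achieved.

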11.8 Power for analysis of key secondary variables

Power for key secondary variables doesn't apply since there will be no formal hypothesis testing for the secondary variables.

11.9 Interim analyses

Refer to [Section 3.5](#).

12 Ethical considerations

12.1 Regulatory and ethical compliance

This clinical study was designed and shall be implemented, executed and reported in accordance with the ICH Harmonized Tripartite Guidelines for Good Clinical Practice, with applicable local regulations (including European Directive 2001/20/EC, US Code of Federal Regulations Title 21, and Japanese Ministry of Health, Labor, and Welfare), and with the ethical principles laid down in the Declaration of Helsinki.

12.2 Responsibilities of the investigator and IRB/IEC

Before initiating a trial, the investigator/institution must obtain approval/favorable opinion from the Institutional Review Board/Independent Ethics Committee (IRB/IEC) for the trial protocol, written informed consent form, consent form updates, subject recruitment procedures (e.g. advertisements) and any other written information to be provided to subjects. Prior to study start, the investigator is required to sign a protocol signature page confirming his/her agreement to conduct the study in accordance with these documents and all of the instructions and procedures found in this protocol and to give access to all relevant data and records to Novartis monitors, auditors, Novartis Quality Assurance representatives, designated agents of Novartis, IRBs/IECs, and regulatory authorities as required. If an inspection of the

clinical site is requested by a regulatory authority, the investigator must inform Novartis immediately that this request has been made.

For multi-center trials, a Coordinating Investigator will be selected by Novartis around the time of Last Patient Last Visit to be a reviewer and signatory for the clinical study report.

12.3 Publication of study protocol and results

The key design elements of this protocol will be posted in a publicly accessible database such as clinicaltrials.gov. In addition, upon study completion and finalization of the study report the results of this trial will be either submitted for publication and/or posted in a publicly accessible database of clinical trial results.

13 Protocol adherence

This protocol defines the study objectives, the study procedures and the data to be collected on study participants. Additional assessments required to ensure safety of subjects should be administered as deemed necessary on a case by case basis. Under no circumstances is an investigator allowed to collect additional data or conduct any additional procedures for any research related purpose involving any investigational drugs under the protocol.

[figure not shown]
Investigators ascertain they will apply due diligence to avoid protocol deviations. If an investigator feels a protocol deviation would improve the conduct of the study this must be considered a protocol amendment, and unless such an amendment is agreed upon by Novartis and approved by the IRB/IEC and health authorities, where required, it cannot be implemented.

ALT or AST elevation with coagulopathy	
ALT or AST $> 3 \times$ ULN and INR > 1.5 (in the absence of anticoagulation)
ALT or AST elevation accompanied by symptoms	
ALT or AST $> 3 \times$ ULN accompanied by (general) malaise, fatigue, abdominal pain, nausea, or vomiting, or rash, or eosinophilia
Isolated ALT or AST elevation	
ALT or AST $> 8 \times$ ULN$5 \times$ ULN $<$ ALT/AST $\leq 8 \times$ ULN$3 \times$ ULN $<$ ALT/AST $\leq 5 \times$ ULN
Isolated ALP elevation	
ALP $> 2 \times$ ULN (in the absence of known bone pathology)
Others	
Any clinical event of jaundice (or equivalent term)Any adverse event potentially indicative of liver toxicity

Table 15-2 Actions required for Liver Events

Criteria	Actions required
Potential Hy's Law case	
ALT or AST elevation with coagulopathy	
 • Discontinue the study treatment immediately
ALT or AST elevation accompanied by symptoms	
 • Hospitalize, if clinically appropriate • Establish causality
Isolated ALT or AST elevation $> 8 \times \text{ULN}$	
 • Complete CRFs per liver event guidance
Jaundice	
Isolated ALT or AST elevation > 5 to $\leq 8 \times \text{ULN}$	
 • If confirmed, consider interruption or discontinuation of study drug • If elevation persists for more than 2 weeks, discontinue the study drug • Establish causality • Complete CRFs per liver event guidance
Isolated ALT or AST elevation > 3 to $\leq 5 \times \text{ULN}$ (patient is asymptomatic)	
 • Monitor liver chemistry tests two or three times weekly
Isolated ALP elevation	
 • Repeat liver chemistry tests within 48-72 hours • If elevation is confirmed, measure fractionated ALP; if $>50\%$ is of liver origin, establish hepatic causality • Complete CRFs per liver event guidance
Any AE potentially indicative of liver toxicity	
 • Consider study treatment interruption or discontinuation • Hospitalize if clinically appropriate • Complete CRFs per liver event guidance

Table 15-3 Exclusion of underlying liver disease

Disease	Assessment
Hepatitis A, B, C, E	
 • IgM anti-HAV; HBSAg, IgM anti-HBc, HBV DNA; anti-HCV, HCV RNA, IgM & IgG anti-HEV, HEV RNA
CMV, HSV, EBV infection	
 • IgM & IgG anti-CMV, IgM & IgG anti-HSV; IgM & IgG anti-EBV
Autoimmune hepatitis	
 • ANA & ASMA titers, total IgM, IgG, IgE, IgA
Alcoholic hepatitis	
 • Ethanol history, gGT, MCV, CD-transferrin
Nonalcoholic steatohepatitis	
 • Ultrasound or MRI
Hypoxic/ischemic hepatopathy	
 • Medical history: acute or chronic CHF, hypotension, hypoxia, hepatic venous occlusion. Ultrasound or MRI.
Biliary tract disease	
 • Ultrasound or MRI, ERCP as appropriate.
Wilson disease	
 • Caeruloplasmin
Hemochromatosis	
 • Ferritin, transferrin
Alpha-1-antitrypsin deficiency	
 • Alpha-1-antitrypsin

16 Appendix 2: Specific Renal Alert Criteria and Actions

Table 16-1 Specific Renal Alert Criteria and Actions

Criteria	Action required
Serum creatinine (sCr) increase 25 – 49% compared to baseline	
 Consider causes and possible interventions Follow up within 2-5 days
Serum creatinine increase $\geq 50\%$	
 Consider causes and possible interventions Repeat assessment within 24-48h if possible Consider drug interruption or discontinuation unless other causes are diagnosed and corrected Consider hospitalization and specialized treatment
Protein-creatinine or albumin-creatinine ratio increase ≥ 2 -fold or new onset dipstick proteinuria $\geq 1+$ or Albumin-creatinine ratio (ACR) ≥ 30 mg/g or ≥ 3 mg/mmol; or Protein-creatinine ratio (PCR) ≥ 150 mg/g or >15 mg/mmol	
 Consider causes and possible interventions Assess serum albumin & serum protein Repeat assessment to confirm Consider drug interruption or discontinuation unless other causes are diagnosed and corrected
New onset glucosuria on urine dipstick (unless related to concomitant treatment, diabetes)	Assess & document: 
 Blood glucose (fasting) Serum creatinine Urine albumin-creatinine ratio
New hematuria on dipstick	Assess & document: 
 Urine sediment microscopy Assess sCr and urine albumin-creatinine ratio Exclude infection, trauma, bleeding from the distal urinary tract/bladder, menstruation Consider bleeding disorder

Additional specialized assessments are available to assess renal function or renal pathology. (Note: In exceptional cases when a nephrologist considers a renal biopsy, it is strongly recommended to make specimen slides available for evaluation by Novartis to potentially identify project-wide patterns of nephrotoxicity.)

Whenever a renal event is identified, a detailed subject history and examination are indicated to identify, document and potentially eliminate risk factors that may have initiated or contributed to the event:

- Blood pressure assessment (after 5 min rest, with an appropriate cuff size)
- Signs and symptoms such as fever, headache, shortness of breath, back or abdominal pain, dysuria, hematuria, dependent or periorbital edema
- Changes in blood pressure, body weight, fluid intake, voiding pattern, or urine output
- Concomitant events or procedures such as trauma, surgical procedures, cardiac or hepatic failure, contrast media or other known nephrotoxin administration, or other potential causes of renal dysfunction, e.g., dehydration, hemorrhage, tumor lysis

Table 16-2 Follow-up of renal events

Action	Follow up
Assess*, document and record in the Case Report Form (CRF) or via electronic data load. Review and record possible contributing factors to the renal event (co-medications, other co-morbid conditions) and additional diagnostic procedures (MRI etc) in the CRF.	
• Urine dipstick and sediment microscopy• Blood pressure and body weight• Serum creatinine, electrolytes (sodium, potassium, phosphate, calcium), bicarbonate and uric acid• Urine output 
or
 
• Event resolution: (sCr within 10% of baseline or protein-creatinine ratio within 50% of baseline)
Monitor subject regularly (frequency at investigator's discretion) until:	
• Event stabilization: sCr level with $\pm 10\%$ variability over last 6 months or protein-creatinine ratio stabilization at a new level with $\pm 50\%$ variability over last 6 months.

* Urine osmolality: in the absence of diuretics or chronic kidney disease this can be a very sensitive metric for integrated kidney function that requires excellent tubular function. A high urinary osmolality in the setting of an increase in sCr will point toward a “pre-renal” cause rather than tubular toxicity.

Clinical Development
LIK066
Clinical Trial Protocol CLIK066B2203 / NCT03198767

**Randomized, open label, two-part, three-period,
cross-over study to investigate the effects of carbohydrate
in diet and to evaluate supplements on the gastrointestinal
tolerability of LIK066 in overweight or obese subjects**

Statistical Analysis Plan (SAP)

Author: Trial Statistician, [REDACTED]

Document type: SAP Documentation

Document status: v02

Release date: 27-Sep-2017

Number of pages: 19

Property of Novartis
For business use only
May not be used, divulged, published or otherwise disclosed
without the consent of Novartis

Document History – Changes compared to previous final version of SAP

Date	Time point	Reason for update	Outcome for update	Section and title impacted (Current)
21-June-2017	Prior to DB lock	Creation of initial version	N/A – First version	NA
21-Sep-2017	Prior to DB lock	Study conduct issues	Daily number of bowel movements is added as another variable for the primary endpoint, three-day total number of bowel movements is added as another variable for the secondary endpoint	Section 6.1
21-Sep-2017	Prior to DB lock	Study conduct issues	Method to impute missing urine volume is updated	Section 6.3.3.1

Table of contents

Table of contents	3
List of tables	4
1 Introduction	5
1.1 Scope of document	5
1.2 Study reference documentation	5
1.3 Study objectives.....	5
1.3.1 Primary objective(s)	6
1.3.2 Secondary objective(s)	6
[REDACTED] [REDACTED]	6
1.4 Study design and treatment.....	7
2 First interpretable results (FIR)	8
3 Interim analyses.....	8
4 Statistical methods: Analysis sets.....	8
[REDACTED]	9
[REDACTED] [REDACTED]	9
[REDACTED] [REDACTED]	10
[REDACTED] [REDACTED]	10
6 Statistical methods for Pharmacodynamic (PD) parameters	10
6.1 Primary objective.....	10
6.1.1 Variables	10
6.1.2 Descriptive analyses	10
6.1.3 Statistical model, assumptions and hypotheses.....	11
6.2 Secondary objectives	12
6.2.1 Variables	12
6.2.2 Descriptive analyses	12
6.2.3 Statistical model, assumptions and hypotheses.....	12
[REDACTED]	13
[REDACTED] [REDACTED]	13
[REDACTED] [REDACTED]	14
[REDACTED] [REDACTED]	15

7	Statistical methods for safety and tolerability data.....	15
7.1	Variables	15
7.2	Descriptive analyses	15
7.3	Graphical presentation	17
9	Reference list.....	19

List of tables

Table 4-1 Protocol deviation codes and analysis sets..... 9

1 Introduction

1.1 Scope of document

The RAP documents contain detailed information to aid the production of Statistics & Programming input into the Clinical Study Report (CSR) for trial “**CLIK066B2203**”.

The Statistical analysis plan (SAP) describes the implementation of the statistical analysis planned in the protocol.

1.2 Study reference documentation

Protocol version used for this SAP is final version v01 dated 08-Aug-2017.

